4.4 MIXED INCLUSION & EXCLUSION CRITERIA FOR TUBERCULIN CHALLENGE ARM ONLY

VOLUNTEERS WITH LATENT TB INFECTION

INCLUSION CRITERIA

- Males and females aged 18 to 60 years
- Body mass index in the range 18-39
- Positive blood Interferon- γ release assay (IGRA): Quantiferon TB Gold-in-Tube (QFT-it), **>0.35 IU/ml** IFN- γ versus control

- Tuberculin skin test (TST), using RT23 tuberculin purified protein derivative (PPD), from Statens Serum Institut (SSI) of Copenhagen.
- 2 tuberculin units (TU) in 0.1ml injected intradermally (id) : **≥6mm to ≤25mm** of induration at 48-120h OR **≥15mm to ≤25mm** in subjects with BCG vaccination
- Normal chest X-ray (CXR) or CT scan if performed routinely for clinical reasons
- Previous chemoprophylaxis for TB is permitted.

HEALTHY INTERFERON- γ RELEASE ASSAY (IGRA) NEGATIVE VOLUNTEERS

INCLUSION CRITERIA

- Age and sex matched to latent TB subjects
- Body mass index in the range 18-39
- No clinical history of TB infection
- Healthy with no lung nor systemic symptoms
- No active nasal allergy
- No BCG vaccination
- Negative blood Interferon- γ release assay (IGRA): Quantiferon TB Gold-in-Tube (QFT-it), **<0.35 IU/ml** IFN- γ versus control
- Tuberculin skin test (TST), using RT23 tuberculin purified protein derivative (PPD), from Statens Serum Institut (SSI) of Copenhagen.
- 2 tuberculin units (TU) in 1ml injected intradermally (id): **≤6mm** of induration at 48-120h.
- Chest X-ray is not required

EXCLUSION CRITERIA (FOR ALL VOLUNTEERS)

Nasal and Respiratory

- Recent infections in past 14 days before screening: especially upper respiratory tract illnesses (including colds and influenza), sore throats, sinusitis, infective conjunctivitis.
- Lower respiratory tract infection in past 28 days
- Signs or symptoms of significant nasal anatomical defects, hypertrophy of turbinates, major septum deviation, nasal polyposis or recurrent sinusitis
- Nasal mucosal defects, injury, ulceration
- Previous nasal or sinus surgery
- No clinical history of allergic rhinitis, allergic asthma or eczema.

Concomitant diseases

- Active tuberculosis at any stage in life
- ENT disease
- Active infectious disease including hepatitis
- Respiratory disease
- Renal disease
- Autoimmune disease
- Rheumatological disease & vasculitis
- Dermatological disease
- Neoplastic conditions

- Metabolic diseases and extreme obesity
- Severe depression and psychiatric disorders

Therapy

- Medical therapy other than that permitted for contraception or for chronic conditions unlikely to affect the results of the study as determined by the study physician.
- Treatment with local or systemic corticosteroids during the previous 2 months
- Anti-inflammatory therapy: including non-steroidal anti-inflammatory drugs (NSAIDs)

Miscellaneous

- Participation in a therapeutic drug trial in the prior 30 days.
- Inability or unwillingness to use contraception if the patient is female of child-bearing age.
- Pregnant or breast feeding women
- Inability to provide informed consent

NB: Smokers permitted – but must be willing to stop smoking for duration of the study

4.5 WITHDRAWAL CRITERIA

In the case of the ascending dose tolerability studies, all clinical activities will discontinue if there is a significant level of adverse events that is judged to be related to the nasal challenge as judged by the patient, and in the opinion of the Study Physician and/or the Principal Investigator.

5. ADVERSE EVENTS

5.1 DEFINITIONS

Adverse Event (AE): any untoward medical occurrence in a patient or clinical study subject.

Serious Adverse Event (SAE): any untoward and unexpected medical occurrence or effect that:

- **Results in death**
- **Is life-threatening** – *refers to an event in which the subject was at risk of death at the time of the event; it does not refer to an event which hypothetically might have caused death if it were more severe*
- **Requires hospitalisation, or prolongation of existing inpatients' hospitalisation**
- **Results in persistent or significant disability or incapacity**
- **Is a congenital anomaly or birth defect**

Medical judgement should be exercised in deciding whether an AE is serious in other situations. Important AEs that are not immediately life-threatening or do not result in death or hospitalisation but may jeopardise the subject or may require intervention to prevent one of the other outcomes listed in the definition above, should also be considered serious.

5.2 REPORTING PROCEDURES

All adverse events should be reported. Depending on the nature of the event the reporting procedures below should be followed. Any questions concerning adverse event reporting should be directed to the Chief Investigator in the first instance.

5.2.1 Non serious AEs

All such events, whether expected or not, should be recorded.

5.2.2 Serious AEs

An SAE form should be completed and faxed to the Chief Investigator and the Sponsor within 24 hours. However, relapse and death due to an independent condition, and hospitalisations for elective treatment of a pre-existing condition do not need reporting as SAEs.

All SAEs should be reported to the NRES Committee London-Harrow where the Chief Investigator considers the event was:

- 'related', i.e. resulted from the administration of any of the research procedures; and
- 'unexpected', i.e. an event that is not listed in the protocol as an expected occurrence

Reports of related and unexpected SAEs should be submitted within 15 days of the Chief Investigator becoming aware of the event, using the NRES SAE form for non-IMP studies. The Chief Investigator must also notify the Sponsor of all SAEs.

Local investigators should report any SAEs as required by their Local Research Ethics Committee, Sponsor and/or Research & Development Office.

Contact details for reporting SAEs

[contact], attention [name] and/or [name]
Please send SAE forms to: Imperial Clinical Respiratory Research Unit (ICRRU)
St, Mary's Hospital
[name]
Paddington
[name]
[contact] (Mon to Fri 09.00 – 17.00)

6. ASSESSMENT AND FOLLOW-UP:

DOSAGE JUSTIFICATION

SAFETY MEASURES

SAMPLING SCHEDULE

MPLA

We are proposing nasal administration of MPLA at incremental ascending single doses from 10 to 100 to 500µg/100µl/nostril.

- We have recently completed a study in 15 subjects with nasal highly purified LPS at doses of up to 100µg (in 100 µl), in which there were no symptoms or adverse events caused by the nasal LPS.
- MPLA is at least 100 fold less toxic than LPS, and has been administered to more than 300,000 human subjects.

- MPLA has been used as an allergen immunotherapy adjuvant at doses of 50µg sublingually and by subcutaneous injection (36;46;47).
- MPLA has been given to rodents at doses of 2500µg/kg by injection (81).

Poly-IC

Poly-IC is a synthetic viral poly-inosine/cytosine molecule that stimulates TLR-3. Unmodified poly-IC given systemically for cancer caused toxic side effects and this was probably caused by IL-12 production (82). High molecular weight poly-IC is employed for *in vitro* stimulation of human cells at doses of 5-100 µg/ml (83) (84) (85) (86) (87).

- A pilot study of Poly-IC nasal challenge was published recently by a group from Lund University, Sweden (53). Seven healthy atopic volunteers were challenged with a total of 800µg Poly-IC, administered as 8 separate doses of 100µl into one nostril. Four doses were given over an hour on day 1 and four doses 24h later on day 2. Each volunteer was challenged twice - once outside the allergen season and once during the Swedish birch pollen allergy season. The challenge was tolerated well, causing no changes in total nasal symptom scores at this dose. Nasal lining cells (epithelial cells) were taken using an interdental brush, and the RNA levels analysed.
- Our study similarly will recruit healthy volunteers, both atopic and non-atopic. We will not recruit atopic volunteers during allergy season, to avoid any confounding effects of allergy on results. Our study will have additional scientific merit to that published as we repeatedly sample the mucosal lining fluid and look directly at the proteins secreted, as well as the RNA. Alongside total nasal symptom scores, we also assess volunteer responses using peak nasal inspiratory flow measurements. This will allow both subjective and objective clinical measurements that we can correlate with the immune data generated.
- Based on the successfully tolerated dosage with measurable mucosal immune responses reported by Brandelius et al. (53), we therefore propose omitting Part A (Poly-IC incremental dose escalation from 10µg to 500µg) from the study, and move directly onto Part B with Poly-IC top dose 500µg. We intend to administer a total of 500µg Poly-IC into each nostril over 1 hour, in 5 equal doses.

Poly-ICLC

Poly-ICLC is poly-IC stabilised with poly-L-lysine and carboxymethylcellulose, and this molecule has more RNase resistance, and is better able to stimulate intracellular endosomal TLR3. Poly-ICLC has been developed by a Pharmaceutical Company (Oncovir of Washington DC, USA) and has been administered to man in a range of clinical studies, including as a vaccine adjuvant (48;54).

We propose to administer poly-ICLC at incremental ascending single nasal spray doses from 10 to 100 to 500µg to 1000µg/in up to 500µl, topically onto the nasal mucosa. We have obtained poly-ICLC from Oncovir and will use doses previously well tolerated in man.

- On the basis of skin and nasal tuberculin doses being in the same range, we shall give tuberculin at a top dose of 10TU/100µl spray.
- Bronchial installation: Tuberculin has been administered safely to subjects with latent TB by bronchosegmental challenge at 0.5TU per 10ml.

In the studies of Richard Silver and colleagues in Ohio, 0.5TU tuberculin PPD was administered into a subsegment of the lingula in 10ml, covering an area of alveoli and small airways estimated at 100cm² (58) (59) (60).

We estimate our nasal spray is delivered over each nostril to an equivalent area of approximately 100cm², that corresponds to the area of the nasal mucosa in a nostril. Hence we begin at a lower dose of 0.1TU per nostril spray.

Allergen

The dose of Timothy grass pollen allergen has previously been safely employed in a range of clinical studies in patients with allergic rhinitis and asthma (91).

Vitamin D3

This is a widely used nutritional supplement with an excellent safety profile with no adverse events reported at doses of 2000-4000 IU/day given orally. To study the actions of vitamin D3 we propose looking at the effects of NAC with Timothy grass pollen in people with grass pollen allergy outside the summer grass pollen season (May-July).

We will use Vitamin D3 at a dose of 4000IU/tablet taken orally. This dose has been widely used in research studies and was used on a daily basis for 28 days in the VIDA Study: Vitamin D Supplementation in Asthma (65). There is no additional effect of increasing the dose further and very few studies go above 4000IU/day.

The supplement used will be sourced from Lamberts Healthcare Ltd and is certified to be

- Manufactured according to good medical practice guidelines (GMP)
- Verified for quality (vitamin D levels) to British Pharmacopoeia (BP) standards
- Licensed as a food supplement

Serum calcium levels will be monitored as rarely hypercalcaemia can be an adverse event.

Placebo

This will be prepared by an NHS pharmacy in a similar format to vitamin D3 and will be taken by subjects in an identical manner to the vitamin D3 supplementation.

DOSING SCHEDULE: SAFETY PRECAUTIONS

A. Nasal Challenge with TLR-Agonists

Then the second subject will be observed over **≥48h**, again only proceeding if there are no adverse events in the first 2 subjects

Then the 3rd and 4th subjects can be given nasal challenge simultaneously.

There will be follow-up for all subjects given nasal challenge at 7d after challenge.

Ascending Dose Protocol in Subjects with Latent TB (LTB)

Single dose of tuberculin PPD per subject (spray each nostril),
4 subjects per dose without placebo initially, 4 groups of 4:

- 0.1TU/nostril, from tuberculin 20U/ml, n=4
clinical observations: nasal examination and systemic features (BP, pulse, temperature) every 30min for 2h
- 1.0TU/nostril, from tuberculin 20U/ml, n=4
clinical observations, nasal examination and systemic features (BP, pulse, temperature)
- 2.0TU/nostril, from tuberculin 20U/ml, n=4
clinical observations, nasal examination and systemic features (BP, pulse, temperature)
- 5.0TU/nostril, from tuberculin 100U/ml, n=4
clinical observations nasal examination and systemic features (BP, pulse, temperature)

After 5.0TU has been administered clinical data and MSD analyses of nasosorption eluates from all doses will be made.

Then the decision will be made on whether to continue 5.0TU nostril or move up to 10.0TU/nostril, from tuberculin 100U/ml

Highest dose nasal tuberculin cohort

1. Decision on top dose.
N=8 on top dose with latent TB, 6 versus 2 placebo
N=8 healthy IGRA test negative, 6 versus 2 placebo
2. Nasosorption:
 - cytokines and chemokines: - elute with buffer
 - lipidomics, prostanoids, resolvins, metabolomics – spin off neat
3. Nasal scrapes for:
 - flow cytometry on T cells and DCs
 - transcriptomics

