Appendix 3A

Part A: Tuberculin nasal challenge ascending dose study based on clinical tolerability and levels of soluble inflammatory mediators

4 Cohorts of 4 latent TB subjects *One cohort per dose, single dose per subject*

Safety & Dosing Tolerability

Nasal mucosa examination, nasal & systemic symptoms checked every 30m for 2h after challenge

- 1st subject challenged & observed for 4d
- If dose well tolerated, 2nd subject challenged & observed for 2d
- If dose well tolerated, then 3rd & 4th subjects challenged, observed for 4d before next cohort

Screening

- Blood QFT-it +ve
- TST ≥ 6 mm to ≤ 25 mm
- CXR
- Nasal curettage
- ECG
- Bloods

Nasal
Challenge
100 μ l

Clinic
Visit

Clinic
Visit

Clinic
Visit

Clinic
Visit

Clinic
Visit

d-7

d0

d1

d2

d3

d4

d7

Nasal Challenge Procedures

- Initial bilateral lavage
- PNIF and nasal symptoms: d-7, -30m, 1-8h, d1-d4, d7
- Nasal SAM, neat & eluate: d-7, -30m, -10m, 1-8h, d1-d4, d7
- Nasal curettage: d-7, d2, d4, d7 (up to 4/timepoint)

Nasal challenge RT23 PPD

Dosing regime

- 0.1 TU in 100 μ l, n=4
- 1.0 TU in 100 μ l, n=4
- 2.0 TU in 100 μ l, n=4
- 5.0 TU in 100 μ l, n=4

Nasal SAM, neat:

[figure not shown]
- Mass Spectrometry
- Lipidomics
- Prostanoids

Nasal SAM, eluate:

[figure not shown]
- Cytokines & chemokines

Nasosorption mediator analysis after clinical phase of study up to 5.0TU. Curettage for transcriptomics only.

[figure not shown]

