2. STUDY OBJECTIVES

2.1 PRIMARY AND SECONDARY OBJECTIVES

- To develop a set of well-tolerated, robust and reproducible (validated) nasal challenge systems with microbial constituents and allergen. To identify biomarker signatures following different challenges.

- To document a dose response and time course to nasal challenge in terms of cytokine and chemokine release, and nasal epithelial curettage (Rhinoprobe) mRNA expression, cell influx by flow cytometry.
- To provide a set of nasal challenge methods to enable a “proof of target pharmacology” for a novel therapy or vaccine. This may also permit dosage optimisation in relation to clinical efficacy studies.
- To develop real time sampling utilising a special probe that touches the surface of the nasal lining and is linked to a mass spectrometer.

To assess nasal cytokines/chemokines in the nasal mucosa and assess levels of circadian-associated gene expression (BMAL-CLOCK genes) in curettage samples after NAC before and after Vitamin D supplementation.

3. STUDY DESIGN (See Figures above)

Group 1: Nasal challenge with TLR Agonists: This part of the study has a total of 96 subjects divided into two parts; Part A and B.

Part A: We shall have 3 cohorts of 8 healthy volunteers (4 of the 8 having atopy). There will be a separate cohort of 8 subjects for each challenge agent (MPLA, poly-ICLC, and resiquimod).

A careful incremental ascending dose tolerability study will be performed: starting with saline and then giving single doses of 10, 100, 500µg and up to 1000µg of a given challenge agent in volumes ranging from 100µl to 500µl per nostril.

Part A, N= 24

- | | |
|---------------|-------|
| a. MPLA | n = 8 |
| b. Poly-ICLC | n = 8 |
| c. Resiquimod | n = 8 |

For each challenge agent we shall initially take serial SAM samples over 8 hours, and assess the cytokine and chemokine response.

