7. STATISTICS AND DATA ANALYSIS

Data and all appropriate documentation will be stored for a minimum of 10 years after the completion of the study, including the follow-up period.

The major data will be levels of cytokines and chemokines in nasal SAM eluates.

We shall perform a test of distribution of data (Shapiro-Wilks test), although nasal levels of chemokines and cytokines are generally non parametric in distribution.

Raw Data:

We shall make plots for individual cytokines with raw data for individuals connected by lines. These “spaghetti plots” generally have different colours for different individuals.

Summary Statistics

Normal data with graphs with means and standard error of means (SEM)

Non-normal data with graphs with medians, quartiles and ranges (box-whisker)

Non-parametric tests are used to compare challenge effects with placebo at different times:
Willcoxon signed-rank test for paired and Mann-Whitney for unpaired data.

The differences from baseline and difference compared with that from placebo (active-placebo) at each time point and the differences from placebo (active-placebo) will be calculated, and the significance determined.

We shall also analyse area under the curve (AUC), by selecting specified times in the early or late phase or for the entire response.

e.g. PGD2 from 10min to 2h

e.g. for IL-4 at 4 to 8h.

A *P* value of <0.05 is considered significant.

Randomization

For the ViDAR study randomization will be supervised by the pharmacy at St Mary’s Hospital. The pharmacy will organise the packaging and have sole access to the randomization codes until the completion of all the clinical aspects of the study.

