Appendix 3a: Part A Summary of Procedures for Tuberculin Nasal Challenge

PART A: Nasal ascending dose (0.1TU, 1.0TU, 2.0TU, 5.0TU) tolerability and SAM

Time 3a	S D -7	-30m	-20m	-10m	Nasal Challenge (NC)	1h – 8h	d1	d2	d3	d4	d7
Nasal challenge Saline/Tuberculin (variable doses)					X	X					
Bilateral nasal lavage for washing purposes	X		X			X					
Nasal mucosal examination		X				X	X	X	X	X	X
Total nasal symptom scores (TNSS) & PNIF		X				X	X	X	X	X	X
Nasosorption		X 2L 2R		X 2L 2R		X 2L 2R	X 2L 2R	X 2L 2R	X 4L	X 4R	X 4R
OPTIONAL Nasal curettage	X							X 4R		X 4L	X 4R

- LEFT nostril: Nasosorption neat: to include from lipidomics, mass spectrometry, prostanoids, PGD2, tryptase
- RIGHT nostril: Nasosorption in assay buffer: for chemokines and cytokines

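### Section 7 plans no between-dose analysis for tuberculin Part A, which has no placebo, although dose response is an objective

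*Combined protocol and SAP*

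**What the plan says.** The Appendix 3A diagram describes tuberculin Part A as "One cohort per dose, single dose per subject", with four cohorts of 4 subjects with latent TB at 0.1, 1.0, 2.0 and 5.0 TU per nostril. The ascending-dose text in Section 6 gives the same structure, "4 subjects per dose without placebo initially, 4 groups of 4". Placebo first appears in the highest-dose cohort, at 6 active and 2 placebo in each of two groups.

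Section 2.1 lists as an objective "To document a dose response and time course to nasal challenge in terms of cytokine and chemokine release". Section 6 adds that, once 5.0 TU has been given, clinical data and mediator results from all doses are analysed. The choice between staying at 5.0 TU and moving to 10.0 TU follows. It does not say how the mediator results count in that choice.

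Section 7 says "Non-parametric tests are used to compare challenge effects with placebo at different times" and names "Willcoxon signed-rank test for paired and Mann-Whitney for unpaired data". It also plans differences from baseline, active-minus-placebo differences at each time point, and AUCs over selected windows. A P "value of <0.05 is considered significant". No contrast between doses, trend test or dose-response model appears.

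Two schedule entries disagree. The Part A table in Appendix 3a has a row "Nasal challenge Saline/Tuberculin (variable doses", which sits badly with a design that has no placebo. The Appendix 3A diagram lists "Nasal SAM, neat & eluate: d-7, -30m, -10m, 1-8h, d1-d4, d7", but the nasosorption row of the Appendix 3a table has no d-7 entry.

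**The concern.** The stated question for Part A is how the mediator response changes with dose. The stated tests answer a different one, active against placebo, and Part A has no placebo group for them to use. The other planned contrast, change from baseline, shows whether a response occurred but not whether it depends on dose. If it is tested cohort by cohort with the named paired test, it cannot reach the 0.05 threshold at all.

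The mediator results from the four doses are therefore due for review at an important decision with no agreed way to judge whether they rise with dose. If the comparison is chosen after the data are seen, the choice of mediator, time point and pair of cohorts is open. That invites selective reading of groups of 4.

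**Working it through.** **Inputs from the documents.** Four cohorts of 4, one dose each (Appendix 3A diagram; Section 6); doses 0.1, 1.0, 2.0 and 5.0 TU; tests and the 0.05 threshold from Section 7. Sidedness is not stated, so two-sided is assumed. The plan gives no power, effect size or SD, so there is no figure of its own to reproduce.

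**Step 1: smallest attainable exact P, without ties.**
- Signed-rank against baseline in one cohort: 2/2^4 = 0.125 (one-sided 1/2^4 = 0.0625). Neither reaches 0.05.
- Signed-rank pooled over 16 subjects: 2/2^16 = 0.00003. This can be significant, but it tests for any response, not a dose response.
- Mann-Whitney of two cohorts, 4 v 4: 2/C(8,4) = 2/70 = 0.029, reached only with complete separation. It cannot meet a Bonferroni limit for three pairs (0.05/3 = 0.0167) or six (0.05/6 = 0.0083). All six pairs unadjusted give a 12.6% chance of at least one false positive per mediator and time point (simulated).

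**Step 2: exact trend test.** The Jonckheere-Terpstra statistic J counts the pairs of subjects from different cohorts in which the higher dose has the higher value. There are 6 pairs of cohorts and 4 x 4 = 16 subject pairs in each, so J runs from 0 to 96. Its null distribution covers 16!/(4!)^4 = 63,063,000 arrangements. Rejecting at J >= 70 or J <= 26 gives an exact two-sided size of 0.043.

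**Step 3: power.** Simulated with normal errors on a transformed scale. The total rise from 0.1 to 5.0 TU, in between-subject SD, is an assumption. Equal steps means one third of the rise per dose step. The log-linear shape follows the actual log10 steps of 1.00, 0.30 and 0.40.

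| Total rise | Trend test, equal steps | Trend test, log-linear | Mann-Whitney, 5.0 v 0.1 TU | Mann-Whitney, 5.0 v 2.0 TU (equal steps) |
|---|---|---|---|---|
| 1 SD | 24% | 22% | 14% | 4% |
| 1.5 SD | 49% | 43-44% | 29% | 5-6% |
| 2.25 SD | 83% | 76% | 59% | 9% |
| 3 SD | 97% | 93% | 83% | 14% |

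**Step 4: where the trend test is weak.**
- At a total rise of 2 SD its power is 73% for equal steps and 74% for a curve flat from 2 to 5 TU. Rejection does not tell the two shapes apart.
- If only 5.0 TU responds, its power is about 32%, 50% and 59% at 1.5, 2.25 and 3 SD. At the two larger rises that is below the Mann-Whitney column for 5.0 v 0.1 TU.

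**The case against.** The strongest reply is that Part A is a tolerability escalation, and its objective is to document a dose response, not to test one. Section 7 does plan individual plots, medians with quartiles, and AUCs, and Section 6 reviews all doses together. A descriptive reading of cohorts of 4 could meet that aim. This has weight: the data are not discarded. But Section 7 also sets a significance threshold and names tests, and none of them is directed at dose.

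A reader might infer that Part A has no usable test and cannot show an effect. The documents do not support that. Mann-Whitney is a named test and, if extended to pairs of doses, could reach 0.029. A baseline comparison pooled over 16 could be significant. Section 7 does not say that baseline changes are tested cohort by cohort, nor does it tie them to the signed-rank test alone. The 0.125 floor applies to that one reading.

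A reader might also infer that a trend test would settle the choice between 5.0 and 10.0 TU. It would not: it does not separate a rise from a plateau between 2 and 5 TU, and 10 TU lies outside the doses tested.

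Nor is d-7 the only nasosorption sample from a day without challenge, because d1 to d4 and d7 also have none. It is the only one taken before the challenge day, and the table still has pre-challenge samples at -30m and -10m. This mismatch is minor and separate from the missing analysis.

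**Conclusion.** The point holds in a limited form. For tuberculin Part A, Section 7 states no between-dose analysis, its named tests refer to a placebo that Section 6 says is absent, and the paired test inside a cohort of 4 cannot go below P = 0.125. A trend test over all 16 subjects suits the question better and costs almost nothing. For steadily rising responses it gains about 14 to 24 percentage points of power over the top-v-lowest comparison at total rises of 1.5 to 3 SD under equal steps, and about 10 to 17 points under a log-linear rise.

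The 0.125 floor and the 0.043 size are exact. The power figures rest on assumed shifts in SD units and normal errors; at a 1 SD rise even the trend test has only 22-24%. The gain also depends on a monotone response without a late jump. Cohorts are sequential and no randomisation to dose is described, so dose is confounded with cohort order whichever test is used.

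If the saline in the Appendix 3a row is a real control, the premise of no placebo changes, so that conflict needs settling first. Nothing here bears on which dose should be used.

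**What to change.** Add to Section 7, for tuberculin Part A:

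1. One pre-specified exact Jonckheere-Terpstra test across the four dose cohorts (n = 16), with sidedness stated. Apply it to the change-from-baseline AUC over one named window for one named primary mediator, and say which pre-challenge sample or samples form the baseline. Label other mediators and windows exploratory; otherwise multiplicity returns.
2. Per-dose estimates with confidence intervals, reported with the trend test at the review after 5.0 TU.
3. The limits in plain words: a monotone response is assumed, dose is confounded with cohort order, and the result neither separates a rise from a plateau between 2 and 5 TU nor informs on 10 TU. State that it is one part of the input to the dose decision, and how mediator results are to be weighed.

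Reconcile the Section 6 statement that Part A has no placebo with the saline entry in the Appendix 3a table. Reconcile the d-7 nasosorption sample in the Appendix 3A diagram with its absence from that table.

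The cost is analysis wording and two schedule corrections. It needs no extra subjects, and if the d-7 sample is kept, it is already in the diagram.
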